5.3 Randomization and Code Breaking Procedures

The list of randomized treatment assignments stratified by gender and IL28B status will be prepared by statisticians at The Emmes Corporation and included in the enrollment module of The Emmes Corporation's Internet Data Entry System (IDES). IDES will assign each subject a treatment code from the list after demographic and eligibility data have been entered into the system. A designated individual at each site will be provided with a treatment key, which links the treatment code to the actual treatment assignment, which will be kept in a secure place.

Instructions for use of the enrollment module are included in the IDES User's Guide. Manual back-up randomization procedures are provided for use in the event that the site temporarily loses access to the Internet or the online enrollment system is unavailable.

Unblinding

Unblinding is unlikely to be necessary for the provision of medical treatment or to otherwise protect the safety of study subjects. In the event that an investigator is concerned that a subject might be put at undue risk by continuing product use, the investigator may discontinue product use by this subject; however, knowledge of the specific product (vaccine or placebo) to which the subject was assigned should not be necessary to guide further follow-up and/or treatment.

The co-principal investigators and/or Independent Safety Monitor (ISM) should be available to review and evaluate any notable reactions. In the case of a medical emergency, the co-principal investigators or ISM may deem it medically necessary to unblind the subject's treatment assignment. If the co-principal investigators or ISM believe that unblinding would benefit the medical care of the subject and time permits, DMID will be consulted prior to unblinding, and concurrence will be obtained.

Otherwise, subjects will be unblinded to their drug only at the close of the trial. Subjects who develop HCV infections or drop out will not be unblinded early. The Data Safety and Monitoring Board (DSMB) may receive data in aggregate and presented by treatment group, but without the treatment group identified. The DSMB may be unblinded to individual study treatment assignments, as needed, to adequately assess safety issues.

5.4 Withdrawal

5.4.1 Reasons for Withdrawal

Subjects may withdraw or be withdrawn for any of the reasons given below. The reason for withdrawal will be recorded in the data collection form. The DSMB may recommend withdrawal of subjects.

In accordance with the current revision of the Declaration of Helsinki (amended October 2000, with additional footnotes added 2002 and 2004) and any other applicable regulations, a subject has the right to withdraw from the study at any time and for any reason and is not obliged to give his or her reasons for doing so. The Investigator may withdraw the subject at any time in the interests of the subject's health and well-being. In addition the subject may withdraw/be withdrawn for any of the following reasons:

- Administrative decision by the Investigator.
- Ineligibility (either arising during the study or retrospective, having been overlooked at screening).
- Significant protocol deviation.
- Subject non-compliance with treatment regime or study requirements.
- An adverse event which requires discontinuation of the vaccination regimen or results in inability to continue to comply with study procedures (see below).

If a subject is withdrawn from the study, all study procedures (except for another vaccination) including safety follow-up will be continued, if possible. If voluntary withdrawal occurs, the subject will be asked to continue scheduled study procedures (except for another vaccination) including safety evaluations, if possible, and be given

appropriate care under medical supervision if symptoms of any AE related to participation in the study are continuing. The subject will be followed until the AE is resolved or until the subject's condition becomes stable. (Note: These plans regarding follow-up only apply if the subject received at least one study dose.)

5.4.2 Handling of Discontinuation of Vaccine Regimen

Any subject whose vaccinations have been discontinued will be seen for appropriate follow-up visits or medical care will be arranged until the adverse event has resolved or stabilized.

5.5 Termination of the Study

The NIAID/DMID and/or the FDA have the right to terminate this study at any time. Reasons for terminating the study may include, but are not limited to, the following:

- Incidence or severity of AEs indicating a potential health hazard.
- Data recording is inaccurate or incomplete.
- The Investigator(s) has not been adhering to the protocol or applicable regulatory guidelines in conducting the study.

6 Investigational Products

6.1 Study Products Description

Two investigational vaccines will be used in this study, namely AdCh3NSmut1 and MVA-NSmut, along with the 0.9% sodium chloride as placebo.

AdCh3NSmut1 formulation and dose

The vaccine, AdCh3NSmut1, consists of the attenuated virus, simian adenovirus 3, (AdCh3), encoding the Nonstructural region (NS), from the Hepatitis C virus 1b genotype (BK strain isolate), with a mutation (mut) introduced in the active site of the HCV polymerase.

AdCh3NSmut1 is manufactured under Good Manufacturing Practice (GMP) conditions. The AdCh3NSmut1 vaccine is formulated in A195 buffer (10 mM Tris, 75 mM NaCl, 1 mM MgCl₂, 0.02% PS80, 5% sucrose, 0.1 mM EDTA, 10 mM Histidine, 0.5% ethanol, pH 7.4). AdCh3NSmut1 has been vialed in 2 mL nominal Type I borosilicate glass vial with a siliconized 13 mm butyl rubber stopper at concentration of 5X10¹⁰ vp/mL at 0.5 mL extractable volume /vial. The dose of AdCh3NSmut1 to be used in this study is 2.5x10¹⁰ vp. This dose is obtained by injecting 0.5 mL of the vaccine without dilution.

MVA-NSmut formulation and dose

The vaccine, MVA-NSmut, consists of the attenuated replication-defective orthopoxvirus, modified vaccinia virus Ankara, (MVA), encoding the Nonstructural region (NS) from the Hepatitis C virus 1b genotype (BK strain isolate), with a mutation (mut) introduced in the active site of the HCV polymerase. The investigational medicinal product MVA-NSmut is manufactured under GMP conditions. The investigational medicinal product is supplied as liquid presented in Tris buffer (10 mM Tris, 140 mM NaCl, pH 7.7), at a concentration of 8.9 x 10⁸ plaque-forming units (pfu) per mL. The virus suspension is supplied as sterile 0.5mL/vial extractable volume in 2 mL injection vials, made of clear borosilicate glass, FIOLAX® -klar, WBK 1, DIN ISO 8362/1. The vials were sealed with 13 mm bromobutyl rubber stoppers, grey, FM 457/0, V 9128, SAF 1, DIN ISO 8362-2, aluminium injection closures with a 6 mm hole. **The dose of MVA-NSmut to be used in this study will be 1.8 x 10⁸ pfu delivered intramuscularly. The volume administered will be 0.2 mL without dilution.**

0.9% Sodium Chloride for Injection and Dose

The placebo agent to be utilized will be 0.9% sodium chloride injection, USP which is a sterile, nonpyrogenic, isotonic solution of sodium chloride and water for injection. Each mL contains sodium chloride 9 mg. It is supplied as single-dose containers. The volume to be administered will be 0.5 mL and 0.2 mL without dilution delivered intramuscularly.

A pharmacy facility will be located at the study site and staffed by pharmacists who are licensed to practice in the US. The pharmacy will have adequate space to store sufficient quantities of study placebo product to assure continuous access to all study subjects.

Illustrations of the Test Article outer box labels are provided below:

Study Drug for DMID Protocol 10-0069 Lot # XXXX AdCh3NSmut1 Vaccine

Directions: administer 0.5 mL by intramuscular injection

Store at or below -70°C

Caution: New Drug – limited by United States Law to investigational use.

Study Drug for DMID Protocol 10-0069 Lot # XXXX MVA-NSmut Vaccine

Directions: administer 0.2 mL by intramuscular injection

Store at or below -70°C

Caution: New Drug – limited by United States Law to investigational use.

Study Drug for DMID Protocol 10-0069 Lot # XXXX 0.9% Sodium Chloride

Directions: administer 0.5 mL by intramuscular injection

Store at 20 to 25°C Expires: MM/DD/YYYY

Caution: New Drug – limited by United States Law to investigational use.

Study Drug for DMID Protocol 10-0069 Lot # XXXX 0.9% Sodium Chloride

Directions: administer 0.2 mL by intramuscular injection

Store at 20 to 25°C Expires: MM/DD/YYYY

Caution: New Drug – limited by United States Law to investigational use.

6.1.1 Acquisition

The AdCh3NSmut1 and MVA-NSmut vaccines will be provided by Okairos. The normal saline placebo will be provided by DMID.

Clinical sites will obtain vaccines from the DMID Clinical Agent Repository at Fisher Bioservices.

6.1.2 Product Storage, Stability, and Expiration

Vials of both recombinant viruses are stored frozen at -70°C or below in a clearly marked secure, limited-access storage area with temperature-controlled freezers. Access to the area will be controlled and temperature records will be maintained.

A pharmacy facility will be located at the study site and staffed by pharmacists who are licensed to practice in the US. The pharmacy will have adequate space to store sufficient quantities of study product to assure continuous access to all study subjects.

AdCh3NSmut1 Stability

Research grade purified virus has been stored for 12 months in buffer A195 at -70°C with no significant loss of biological activity. Genetic stability has also been assessed

on a research batch of AdCh3NSmut1, subjected to ten passages in PER.C6 cells and no evidence of genetic instability has been observed.

AdCh3NSmut1shelf life extension plan

The AdCh3NSmut1 clinical lot will have an initial expiry date of 12 months from manufacture. A shelf-life extension program is in place to assign new expiry date to the product. Samples of the clinical lot will be tested by a potency assay, based on *in vitro* infectivity in HEK (human embryonic kidney) 293 cells by the AdCh3 hexon immune staining method. Testing will be carried out for a period of 36 months.

MVA-NSmut Stability

The clinical batch of MVA-NSmut has undergone testing to demonstrate genetic stability of the virus. An initial expiration date of 2 years from date of manufacture was assigned based on the vast stability data for MVA based vectors stored at or below -70°C. Titrations on chicken embryo fibroblast (CEF) cells will be performed in order to check that the titer does not decrease over time. Long term stability testing for MVA-NSmut stored in a freezer (-80°C ±10°C) will be carried out for a period of 36 months to allow the expiration date to be lengthened.

0.9% Sodium chloride for injection

The 0.9% sodium chloride should be stored at a controlled room temperature of 20°C to 25°C (68 to 77°F). The solution should be inspected visually for particulate matter and discoloration prior to administration.

6.1.3 Preparation & Administration

Vaccine administration

On vaccination day, both for priming and boosting administration, vaccines will be allowed to thaw to room temperature. The pharmacist or nurse trained to prepare vaccine will wear gloves. Using aseptic technique, the pharmacist or trained nurse will withdraw the volume specified in Section 6.1 into a 1 mL syringe and add a blinding sleeve. The syringe containing the product must be held at room temperature. Once drawn into the syringe, the vaccine should be administered as soon as possible after preparation as intramuscular injection in the deltoid region of the arm. During administration of the vaccines, medicines and resuscitation equipment will be immediately available for the management of anaphylaxis. All subjects will remain on the unit for at least 30 minutes for observation.

6.1.4 Maintaining Blind for Investigational Product

Vaccine will be prepared by a pharmacist or trained nurse and administered by a blinded vaccine administrator. All study assessments will be performed by blinded study personnel. All other staff, as well as all subjects, will be blinded to treatment assignment.

6.1.5 Accountability/Final Disposition for the Investigational Product(s)

A pharmacist at the study site will receive the study products and store them in a designated secure area within the pharmacy. Access will be restricted to the pharmacist, nurse trained to prepare vaccine and the site monitor. The pharmacist will be responsible for keeping accurate records of the material received. S/he will keep a daily log of the amount of material received, the amount dispensed, and the amount remaining at the end of the study. At the end of the study, the pharmacist will perform the final drug accounting of unused study material on the proper log documents. At the completion of the study, a clinical monitor will review final accountability records. All unused vials should be returned to the DMID Clinical Repository at Fisher BioServices.

The pharmacist or trained nurse will be responsible for dispensing the drug to the blinded vaccine administrator. The pharmacist will be responsible for storing, managing, and dispensing all drug supplies for the study. The pharmacist will be responsible for tracking the flow of all study product in a log book, including managing and logging all supplies in storage, and logging all study product dispensed to subjects. The on-site investigator will oversee the duties of the pharmacist and will be responsible for ensuring that the pharmacist is accountable for these responsibilities.

7 Study Procedures/Evaluations

7.1 Clinical Evaluations

Medical History: Will be obtained by interview of the subjects. Subjects will be queried regarding a history of significant medical disorders of the head, eyes, ears, nose, throat (HEENT), mouth, cardiovascular system, lungs, gastrointestinal tract, liver, pancreas, kidney, urologic, nervous system, blood, lymph glands, endocrine system, musculoskeletal system, skin, and genital/reproductive tract. A history of any allergies, cancer, immunodeficiency, psychiatric illness, and autoimmune disease will be solicited.

Targeted Physical Examination: At screening or Day 0 visit, a targeted physical exam will be performed based on subject's clinical history and height and weight will be collected. Vital signs (temperature, heart rate, respiration and blood pressure) will be collected at screening and prior to each vaccination. The exam will be performed by appropriate study personnel to assess general physical condition and will include the following areas/systems: oral cavity, supraclavicular and axillary lymph nodes, cardiovascular, pulmonary, abdomen, skin.

At visits following the first vaccination a targeted physical examination may be conducted based on interim medical history.

Reactogenicity Assessments: Will include brief history for assessment of AE/SAEs just prior to and following vaccination, which includes an assessment of pain, tenderness, erythema, induration and warmth at the injection site; fever, chills, arthralgia/joint pain, malaise/fatigue, myalgia/body aches, headache, nausea, vomiting and abdominal pain. The vaccination site will be examined at the end of the 30 minute observation period following each vaccination as well as at the Day 3/7 and Day 59/63 clinic visits following each vaccination.

Memory Aids: All subjects will complete a subject memory aid for 8 days following each vaccination (Days 0-7). Subject memory aids will be reviewed with the subject in person or by telephone for AE/SAEs at the Day 1-3 follow-up visit or phone call and at the Day 5-9 clinic visit following each vaccination. Following review, subject memory aids will be discarded.

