3.1.1 Primary Safety Endpoints

The primary endpoints in the evaluation of safety are as follows: (1) occurrence of vaccine-related serious adverse events (SAEs) from the time of first vaccination through the entire study period; (2) occurrence of severe local and/or systemic solicited reactogenicity signs and symptoms in the 8 days (Day 0-7) after each vaccination; and (3) occurrence of clinical safety laboratory adverse events (AEs) assessed at baseline and 1 month following each vaccination. The occurrence of these safety parameters will be assessed by treatment arm (vaccine and placebo).

Signs and symptoms will be categorized as either local (pain, tenderness, erythema, induration and warmth) or systemic (fever, malaise/fatigue, myalgia, headache, nausea, vomiting, chills, arthralgia and abdominal pain). Clinical laboratory measures will include measures of white blood cell (WBC), hemoglobin (HgB), platelets, ALT, and creatinine.

The protocol includes safety evaluations at multiple time points in order to better characterize the impact of the vaccine on the at-risk population. Although the principal goal is safety signal detection in association with the experimental vaccine, these safety data will be an important resource for future clinical trials in this population.

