8.2 Subject Follow-Up

Follow-up visits are scheduled in reference to dosing dates as indicated for each visit window.

8.2.1 Day 3, Visit 2

(Window: Day 1 to 5)

- Current health status will be reviewed and any changes since the last visit will be noted.
- The vaccination site will be examined.
- A targeted physical examination may be performed, if indicated, based on review of current health status.
- Study personnel will review the memory aid information with the subject and record all AE/SAEs and concomitant medications on the appropriate data collection form.
- Counseling on avoidance of HCV and HIV infection, and pregnancy will be conducted.
- Referral to drug treatment and needle exchange programs will be provided.

8.2.2 Day 7, Visit 3

(Window: Day 5 to 9)

- Current health status will be reviewed and any changes since the last visit will be noted.
- The vaccination site will be examined.
- A targeted physical examination may be performed, if indicated, based on review of current health status.
- Study personnel will review the memory aid information with the subject and record all AE/SAEs and concomitant medications on the appropriate data collection form.
- Counseling on avoidance of HCV and HIV infection, and pregnancy will be conducted.
- Referral to drug treatment and needle exchange programs will be provided.

8.2.3 Day 14, Visit 4

(Window: Day 7 to 21)

- Current health status will be reviewed and any changes since the last visit will be noted.
- The vaccination site will be examined if ongoing Memory Aid symptoms are reported after Visit 3.

- A targeted physical examination may be performed, if indicated, based on review of current health status.
- Study personnel will review and record all AE/SAEs and concomitant medications on the appropriate data collection form
- Approximately 23 mL of venous blood will be collected for hematology and biochemistry parameters, as described in Section 7.6.1, and performed by the local laboratory.
- Counseling on avoidance of HCV and HIV infection, and pregnancy will be conducted.
- Referral to drug treatment and needle exchange programs will be provided.

8.2.4 Day 30, Visit 5

(Window: Day 23 to 37)

- Current health status will be reviewed and any changes since the last visit will be recorded.
- A targeted physical examination may be performed, if indicated, based on review of current health status.

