- Subjects will receive a single dose of MVA-NSmut vaccine or placebo per randomized assignment via intramuscular injection in the deltoid muscle of the preferred arm. Following vaccination the injection site will be covered with a sterile dressing and subjects will be observed in the clinic for at least 30 minutes. The vaccination site will be examined, and any AE/SAEs will be assessed prior to discharge from the clinic.
- Subjects will be provided with a memory aid and other study related materials to record daily oral temperature and systemic and local AE/SAEs. Subjects will be encouraged to take their temperature around the same time each day. Subjects will be instructed on how to use the memory aid and how to measure and record AE/SAEs prior to discharge from the clinic. Subjects will be instructed to notify the study center if they develop any severe reactions following vaccination. If the site principal investigator or appropriate sub-investigator deems the reaction severe enough, s/he will give further instructions on the proper course of action, including a return to the clinic for immediate evaluation if appropriate.
- Counseling on avoidance of HCV and HIV infection, and pregnancy will be conducted.
- Referral to drug treatment and needle exchange programs will be provided.

• Subjects who become HCV PCR+ after the 1st vaccine may receive a 2nd vaccine dose. These subjects will return for their Visit 7 and 8 assessments and follow the Confirmed HCV Infection visit schedule outlined in Appendix D.

8.2.6 Day 59 [Target 3 Days Post Second Vaccination], Visit 7

(Window: 1-5 days after receipt of second dose of vaccine)

- Current health status will be reviewed and any changes since the last visit will be noted.
- The vaccination site will be examined.
- A targeted physical examination may be performed, if indicated, based on review of current health status.
- Study personnel will review the memory aid information with the subject and record all AE/SAEs and concomitant medications on the appropriate data collection form.
- Counseling on avoidance of HCV and HIV infection, and pregnancy will be conducted.
- Referral to drug treatment and needle exchange programs will be provided.

8.2.7 Day 63 [Target 7 Days Post Second Vaccination], Visit 8

(Window: 7-21 days after receipt of second dose of vaccine)

- Current health status will be reviewed and any changes since the last visit will be noted.
- The vaccination site will be examined.

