12.6 Study Records Retention

Records and documents pertaining to the conduct of this study, including CRFs, source documents, ICFs, laboratory test results, and medication inventory records, must be retained in a secure storage location by the investigator for at least 2 years after a marketing application is approved for the drug; or, if an application is not approved for the drug, until 2 years after shipment and delivery of the drug for investigational use is discontinued and FDA has been so notified. No study records will be destroyed without prior authorization from NIAID.

13 Quality Control and Quality Assurance

Following a written DMID-accepted site quality management plan, the investigational site is responsible for conducting routine, quality assurance (QA) and quality control (QC) activities to internally monitor study progress and protocol compliance. The Principal Investigator(s) will provide direct access to all trial-related sites, source data/documents and reports for the purpose of monitoring and auditing by the sponsor, and inspection by local and regulatory authorities. The Principal Investigator will ensure all study personnel are appropriately trained and applicable documentations are maintained on site.

The Statistical and Data Coordinating Center (SDCC) will implement quality control procedures beginning with the data entry system and generate data quality control checks that will be run on the database. Any missing data or data anomalies will be communicated to the site(s) for clarification and resolution.

14 Ethics/Protection of Human Subjects

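### After dose 1 the last scheduled memory-aid review can fall on Day 5 or 6 and the aid is then discarded, so up to two days of the Day 0-7 primary safety window may have no daily record

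*Protocol*

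**What the plan says.** The second primary safety endpoint in Protocol 3.1.1 is the "occurrence of severe local and/or systemic solicited reactogenicity signs and symptoms in the 8 days (Day 0-7) after each vaccination". Protocol 7.1 has every subject keep a memory aid for those same eight days. It schedules two reviews per dose, the second "at the Day 5-9 clinic visit following each vaccination", and adds: "Following review, subject memory aids will be discarded".

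The visit schedule sets the actual timing. Visit 3 after dose 1 (8.2.2) has "Window: Day 5 to 9". Visit 8 after dose 2 (8.2.7) has "Window: 7-21 days after receipt of second dose of vaccine". At these visits, "Study personnel will review the memory aid information with the subject and record all AE/SAEs and concomitant medications on the appropriate data collection form". Appendix C, repeated as SAP Table 1, marks memory-aid review at Visits 2, 3, 7 and 8 only.

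Three other places bear on the point:
- Protocol 9.4.4 says the aid is gone over again at later visits and calls when needed, and that symptoms persisting at Day 8 are followed until they resolve.
- Visit 4 (8.2.3) records all AEs and examines the site if memory-aid symptoms are still being reported, but lists no review of the aid.
- Protocol 12.6 says "No study records will be destroyed without prior authorization from NIAID".

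**The concern.** The record that feeds a primary safety endpoint can have its last scheduled review before the endpoint window ends, and the form that would hold the remaining days is then thrown away. SAP 9.3.1 takes the worst grade over the period and splits it into severe against everything else. SAP 9.3 uses subjects with non-missing data as the denominator, and SAP 6.5 plans no imputation that would cover this endpoint. A subject recorded only to Day 5 therefore has a usable worst grade and counts as not severe, whatever happened on Days 6 and 7.

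SAP Tables 53-56 and Listings 9-10 also call for a grade on each day through Day 7, which a Day 5 visit cannot supply. Grade 3 solicited systemic reactions count towards a safety-review trigger of two subjects in Protocol 9.6, so a single unreported reaction could matter.

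**Working it through.** No power or sample-size figure is involved. The check is a count of days.

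**Inputs.** Endpoint window and memory aid: Days 0-7 (Protocol 3.1.1 and 7.1). Visit 3: Day 7 ± 2 (Appendix C), written as Day 5 to 9 in 8.2.2. Visit 8: 7-21 days after dose 2 (8.2.7), shown as +14 in Appendix C. Second review under 7.1: Day 5-9 after each dose.

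**Reproducing the plan's figures.** Days 0 to 7 inclusive make 8 days. 7 − 2 = 5 and 7 + 2 = 9, so 8.2.2 and Appendix C agree.

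**Dose 1: diary days that fall after the visit.**

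| Visit 3 on | Days still to come | Share of 8 days |
|---|---|---|
| Day 5 | 6, 7 | 2/8 = 25% |
| Day 6 | 7 | 1/8 = 12.5% |
| Day 7 | none (Day 7 may be partial) | 0% |
| Day 8 | none | 0% |
| Day 9 | none | 0% |

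So 2 of the 5 permitted days come before the window ends. In each row the day of the visit itself may be only partly recorded.

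**What can still recover those days.** No memory-aid review is scheduled after Visit 3 for dose 1. Visit 4 is targeted at Day 14, which is 14 − 7 = 7 to 14 − 6 = 8 days after the missing entries, and may be as late as Day 21. AEs are taken there, but if the aid was discarded after Visit 3 they come from recall without a daily grid. The later review described in 9.4.4 has nothing left to review.

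**Dose 2.** Under 8.2.7 the earliest visit is 7 days after the dose, so no diary day falls after it. The window in 8.2.7 has 21 − 7 + 1 = 15 permitted days. Only Days 7, 8 and 9 also satisfy 7.1, so 12 of the 15 lie outside the timing that 7.1 states. If 7.1 governed instead, dose 2 would have the same gap as dose 1.

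**Possible effect on the endpoint.** The documents give neither the share of subjects seen on Day 5 nor the frequency of first severe reactions on Days 6-7. As an assumption only, let that frequency be 0.5% to 5% of 270 vaccine recipients:
- all seen on Day 5: 270 × 0.005 = 1.35 to 270 × 0.05 = 13.5 subjects at risk of being missed;
- 20% seen on Day 5: 0.2 × 1.35 = 0.27 to 0.2 × 13.5 = 2.7 subjects.

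The upper end is a bound. It requires frequent late-onset severe reactions, no capture by any other route, and every subject attending on the first permitted day.

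**The case against.** The strongest reply is that nothing in the protocol closes the record at Visit 3. Subjects must complete all eight days, and the discard instruction can be read as applying once review is finished. Visit 4 still takes AEs, and persisting symptoms are followed. Subjects are told at both vaccination visits to notify the site of severe reactions. The trigger in 9.6 adds related Grade 3 AEs to solicited Grade 3 systemic reactions, so a late event reported by another route still counts if judged related. Blank days would show up: the daily table has a row for unreported entries, and section 13 sends missing data back to sites. All of this stands, and it limits the harm. It does not supply the missing days, because a site queried about Days 6-7 after discarding the aid can answer only from recall.

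Four stronger readings are tempting, and the documents do not support them:
- **That source documents are destroyed in breach of 12.6.** Section 12 derives source forms from the eCRFs, staff transcribe the reviewed information, and no text designates the aid as a source document. 12.6 allows destruction with NIAID authorization, and the sponsor, DMID, is a division of NIAID. The fair statement is that the only contemporaneous daily record is discarded and that no text reconciles this with 12.6.
- **That three of five visit days are too early.** A Day 7 visit reaches the last day, though perhaps only part of it.
- **That the HCV001 data show late severe reactions.** Protocol 2.2.3 reports 89% of systemic events resolved by 72 hours and 93% by one week. The remaining 11% and 7% describe persistence, not late onset, and the events were 96% mild and 4% moderate.
- **That the dose 1 against dose 2 comparison is materially biased.** Ascertainment is unequal in principle, but Table 57 is a descriptive within-arm tabulation of none against mild or greater. Only a first symptom on Days 6-7 could be misclassified, and the two active doses use different vectors in any case.

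**Conclusion.** The point holds in a limited form. A site that follows the protocol exactly can finish its last scheduled dose 1 review with up to 2 of 8 days outstanding and then discard the form that would have held them. Those days then depend on recall or spontaneous report, and the safeguard in 9.4.4 cannot operate. Separately, the review timing in 7.1 and the Visit 8 window in 8.2.7 disagree.

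The visit windows are the same in both blinded arms, so the design does not itself create a difference between vaccine and placebo. The likely direction is under-counting in both. The gap is confined to dose 1 under the section 8 windows, and to reactions that begin or become severe on Days 6-7. Its size cannot be derived from the documents and is probably small. The conclusion assumes that the Manual of Procedures, which is not among the documents, contains no rule that fills the gap. It is worth correcting because the endpoint is primary and the remedy is cheap.

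**What to change.** 1. In Protocol 7.1, replace the discard instruction with retention of the completed memory aids, and state how they stand under 12.6.
2. Require the final memory-aid review for each dose to take place after the Day 7 entry is complete. When Visit 3 falls earlier, use the telephone review that 7.1 and 9.4.4 already provide for, while the subject still holds the aid.
3. Reconcile the review timing in 7.1 with the Visit 8 window in 8.2.7 and Appendix C, so that one statement governs dose 2.

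The cost is a wording change in the protocol and Manual of Procedures, filing of at most two forms per subject, and one extra call for subjects seen early. The endpoint, the analysis and the visit schedule can stay as they are.
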